### **b) Inclusion and Exclusion Criteria**

**PATIENTS:** **Inclusion Criteria:** we will include English and Spanish speaking adults ages  $\geq 55$  years ( $\geq 50$  years at Mount Sinai for Stage I only) who have a physician diagnosis of asthma. **Exclusion Criteria:** COPD or other chronic lung condition,  $\geq 15$  pack-years

**CAREGIVERS:** **Inclusion Criteria:** we will include English and Spanish speaking adults ages  $\geq 21$  years who provide formal ( $\geq 6$  continuous months) or informal care to an older adult (age  $\geq 60$  years) with a physician diagnosis of asthma. **Exclusion Criteria:** n/a

**CLINICIANS:** **Inclusion Criteria:** we will include English speaking clinicians from participating clinics (adults ages  $\geq 21$  years). **Exclusion Criteria:** n/a

### **c) Number of Subjects**

In Stage I, a total of 150 subjects (patients, caregivers, providers) will be recruited to participate in focus group sessions and/or cognitive interviews. We will recruit 100 subjects from the IMA clinic and 50 subjects from the UMPA and SLMG practices at SLR. In Stage II, a total of 405 patients will be recruited for this study. We will recruit 175 patients from the Mount Sinai Hospital's IMA and Pulmonary clinics, 175 from all aforementioned sites at the Institute for Family Health, and 100 patients from the Mount Sinai's St.Luke's Roosevelt UMPA, SLMG, and 59th Street practices.

### **d) Study Timelines**

	Protocol Title:	Clinic-based vs. home-based support to improve care and outcomes for older asthmatics
	Principal Investigator Name/Contact Info:	[name], MPH Email: [contact]
	Primary Contact Name/Contact Info	[name]
	Date Revised:	June 13, 2016
	Study Number:	IF1737114, GCO#13-1401, HSM#14-00108

The duration of **Stage I** is 8 months. The duration of **Stage II** is 2 years and 4 months. Patients will be followed from the time of consent from baseline through the 12-month follow up.

### e) Study Endpoints

**Stage I** activities are estimated to close on 11/30/2014. Stage II activities are estimated to close on 12/30/2017. We will follow patients for one year (12 months) or until death. We will continue to track patients throughout hospitalizations or after withdraw from the either study arm.

### f) Procedures Involved in the Human Research

#### **STAGE I. Focus Groups and Cognitive Interviews. (Months 0-8)**

We will conduct focus groups and cognitive interviews with patients, caregivers, and clinicians. We expect to conduct 30 cognitive interviews with stakeholders on the intervention protocols and materials, 9-12 focus groups on this same topic and 8-10 interviews with clinicians focusing on the EMR-decision support tool. Team members will compare notes after conducting two interviews at each site and will revise the protocols, materials, and EMR-screen shots before proceeding to the next round of interviews. Interviews will continue until no further substantive changes are required. We will reimburse subjects \$25 in cash. The table below describes the topics to be discussed in the interviews. At the end of each focus groups or cognitive interview, we will ask participants to complete an Information Sheet. The Information Sheet for patients/caregivers asks about gender, age, race, ethnicity, educational attainment, income, English ability, and age the patient was first told they had asthma. The Information Sheet for providers asks about their gender, role in the clinic, clinical training, work domain, what electronic medical records they have used in the past. The sheet also asks them to rate their knowledge and skills in managing asthma in adults, how helpful Epic is in helping them to manage their patients with asthma, and provide any suggestions for what features could be added to Epic to help them to better manage their patients with asthma.

Research Activity	Topics
30 Cognitive Interviews - One subject per interview - Focus: intervention protocols and materials - Patients, caregivers, and clinicians	
 
- Intervention materials
 
- Clinical protocols
 
- EMR-content and programming
 
- Research data collection
 
- Assembly of materials
 
- Creation of manuals
 

9-12 Focus groups - 8 individuals per focus group	
 
- Asthma symptoms and how they affect your life
 
- Roles and responsibilities of the care coach
 

	Protocol Title:	Clinic-based vs. home-based support to improve care and outcomes for older asthmatics
	Principal Investigator Name/Contact Info:	[name], MPH Email: [contact]
	Primary Contact Name/Contact Info	[name]
	Date Revised:	June 13, 2016
	Study Number:	IF1737114, GCO#13-1401, HSM#14-00108

 
- Focus: intervention protocols and materials
 
- Patients, caregivers, and clinicians
 
	
 
- Clinical intervention protocol – i.e., calls vs. visits, length of calls and visits, optimum number of reminders
 
- Best practices for notifying patients about disease belief misconceptions
 
- Review of optimum patient education materials
 

9-12 Focus groups 
 
- 8 individuals per focus group
 
- Focus: EMR-decision support tool
 
- Clinicians only
 
	
 
- Information required for a patient assessment
 
- Decision support tool
 
- Other support tools to model
 
- Overall program
 

### **STAGE II. Randomized Controlled Trial. (Months 9-36)**

**ACC AND CHW ASTHMA PROGRAM DETAILS.** The ACC and CHW programs for asthma CC/SMS will have the same objectives and provide the same general services. The primary difference will be the location, home or office, in which the bulk of services are provided, and the attendant advantages and disadvantages these locations present. **Note:** the ACC and CHW programs will be developed from existing, successfully operating programs at IFH and MSH, and in the East Harlem and South Bronx communities.

- **Training.** During this **Stage I** there will be a brief orientation to the study for all clinical and non-clinical staff in the participating clinics. The project manager will train the four RAs in all study protocols. The RAs will have appropriate Human Subjects Training Program certification. Our team of experts (Asthma Social Workers, Care Managers, General Internists, and Pulmonologists) will train the ACCs and CHWs. All protocols and materials will be carefully reviewed. A pulmonologist and asthma social worker (overseen by [name]) will conduct the asthma trainings, which will cover basic disease processes and the role of allergens and other triggers, symptom and severity assessments (ACT and peak flow), medications and other management strategies, medication adherence and other self-management behaviors (action plans, trigger avoidance, appointment keeping, etc.). [name] will lead training on home assessment, with a discussion on performing the assessment by patient self-reports (germane to the work of the ACC). [name] will lead the training on chronic illness management (e.g., methods to support adherence, motivational interviewing) and principals of care coordination, and [name] will supplement this with information and methods relevant to the CHW and home-based support. We will include some existing CHWs and CCs for this study, thus limiting additional training to asthma-specific management, basic management of other chronic conditions, and the program protocols. Trainings will include role playing and interviews with actual patients. Complete training will be approximately 60 hours. During **Stage II**, ACC/CHWs will be supervised at regular intervals of program implementation to ensure fidelity to program protocols and to reinforce learning.

 Mount Sinai	Protocol Title:	Clinic-based vs. home-based support to improve care and outcomes for older asthmatics
	Principal Investigator Name/Contact Info:	[name], MPH Email: [contact]
	Primary Contact Name/Contact Info	[name]
	Date Revised:	June 13, 2016
	Study Number:	IF1737114, GCO#13-1401, HSM#14-00108

**RESEARCH COMPONENT DETAILS.** We will conduct a 3-arm, patient-randomized pragmatic clinical trial following older adults with uncontrolled asthma for up to 12 months. We will register the trial at ClinicalTrials.gov.

- **Recruitment.** (*Procedures are described in detail above in #5a.*) Patients will be identified from several EMR reports. Following approval by the PCP, patients will receive a letter about the research study and the upcoming call from the RA. The letter will have a toll-free telephone number to enable patients to call and opt-out. The RA will phone patients to describe the study, recruit, screen for asthma control and eligibility, and schedule for a baseline research interview. All research interviews will take place at the preferred location of the patient (in the clinic or in patients' home).
- **Randomization.** After the RA has completed the baseline research interview, the PM will access a dedicated website that implements the algorithm to obtain the assignment. The PM will notify the ACCs or CHWs that a new patient is assigned to their respective intervention arm. Randomization to the study arms will be made with a 1:1:1 scheme using a dynamic algorithm to minimize imbalance between treatments with respect to important covariates including site and level of asthma control (not well controlled vs. very poorly controlled as per NAEPP guidelines). A minimization technique will be employed (i.e., allocation is assigned to the arm that minimizes an imbalance score calculated based on site and asthma control). **Please note:** at the end of the 12-month study period, patients assigned to the usual care arm will be given the option to meet with a clinic-based care coach.
- **Measures.** Baseline and 12-month interviews in person, 3-month and 6-month interviews by phone.

Outcome	Measure	Comments
Asthma control	ACT	Baseline, 3M, 6M, 12M
Pulmonary function	FEV1; FEV1/FVC (hand-held device)	Baseline, 12M
Asthma related QoL	Mini-AQLQ	Self-report measure - Juniper (1999); Baseline, 3M, 6M, 12M
Resource Utilization	Urgent clinic visits, emergency department visits, and hospitalizations	1) Self-report (Baseline, 3M, 6M, 12M) 2) New York State SPARCS registry (12 mos preceding enrollment, 12 mos post-enrollment)
Asthma Management behavior: Medication Adherence	Medication Adherence Report Scale (MARS)	10 item self-report measure – Cohen (2009); Baseline, 3M, 6M, 12M
	Also working on obtaining pharmacy claims	

 
Mount Sinai
	Protocol Title:	Clinic-based vs. home-based support to improve care and outcomes for older asthmatics
	Principal Investigator Name/Contact Info:	[name], MPH Email: [contact]
	Primary Contact Name/Contact Info	[name]
	Date Revised:	June 13, 2016
	Study Number:	IF1737114, GCO#13-1401, HSM#14-00108

Asthma Management behavior: Inhaler Technique	MDI and DPI inhaler technique	RA observation on placebo device using validated checklist - Manzella (1989); Baseline, 12M.
Asthma Management behavior: Self-Monitoring	Asthma action plan use; Peak Flow Meters	Self-report: Action Plan (y/n), Peak Flow (y/n) Peak Flow Frequency of Use; Baseline, 3M, 12M
Trigger Avoidance	Individual Items	Self-report: allergy cover use, household pets, exposure to cigarette smoke in the home, washing bed sheets in hot water, cleaning dust in home; Baseline, 12M
Environmental Exposure	Urban Environment and Childhood Asthma assessment	Baseline and 12 months
Appointment Keeping	Appointment keeping	Chart review of kept and missed clinic appointments; 1 year before baseline – 12M
Patient Perspectives of Services	CAHPS/HCAHPS	Modified Subscales: Perceived trust, Your Care from Nurses. Overall rating of intervention (Scale 1-10) Baseline, 3M, 12M
Programs expectations/Exit Survey	See attached questionnaire	Exit survey at 12M.

 Mount Sinai	Protocol Title:	Clinic-based vs. home-based support to improve care and outcomes for older asthmatics
	Principal Investigator Name/Contact Info:	[name], MPH Email: [contact]
	Primary Contact Name/Contact Info	[name]
	Date Revised:	June 13, 2016
	Study Number:	IF1737114, GCO#13-1401, HSM#14-00108

Other Measures	Items	Comments
Sociodemographics	
 
• Age
 
• Sex
 
• Race/ethnicity
 
• Education
 
• Income
 
• Insurance type
 
	Interviewer administered at baseline
Social support	
 
• Marital status
 
• Number of household occupants
 
• Lubben social support scale
 
	Interviewer administered at baseline, 12 months
Health literacy	
 
• Newest Vital Sign (NVS)
 
	Baseline
Asthma history	
 
• Age of onset
 
• Intubations
 
• Current asthma medication use
 
	Interviewer administered at baseline
Smoking history	
 
• NHANES items
 
	Interviewer administered at baseline, 12 months
Cognitive function	
 
• Montreal Cognitive Assessment (MoCA)
 
	Interviewer administered at baseline
General health	
 
• SF-1 general health measure
 
	Baseline, 3, 6, 12 months
Co-Morbidities		From EMR abstraction at baseline
Medications currently used		From EMR abstraction at baseline
Depression	
 
• NIH PROMIS Measures for Depression
 
	Interviewer administered at baseline, 6, 12 months
Anxiety	
 
• NIH PROMIS Measures for Depression
 
	Interviewer administered at baseline, 6, 12 months
Physical functioning	
 
• Activities of daily living
 
• Instrumental activities of daily living
 
	Lawton and Brody

- **Statewide Planning and Research Cooperative System (SPARCS) Data.** The researchers will also access data on patients' healthcare use (including: hospitalizations or emergency department visits at hospitals other than Mount Sinai) from the New York State Department of Health's SPARCS data. Please note that all the SPARCS data collected is for research purposes only, and not clinical care.
- **Assessment of Acceptance and Implementation of Intervention.** In the final stages of the program, we will perform qualitative and quantitative assessments of provider acceptance, use, and implementation of the EMR-based decision support and tools,

	Protocol Title:	Clinic-based vs. home-based support to improve care and outcomes for older asthmatics
	Principal Investigator Name/Contact Info:	[name], MPH Email: [contact]
	Primary Contact Name/Contact Info	[name]
	Date Revised:	June 13, 2016
	Study Number:	IF1737114, GCO#13-1401, HSM#14-00108

provider experience communicating with ACCs and CHWs and vice versa, and patient experiences.

**Qualitative** assessments will involve one-to-one, semi-structured, exploratory interviews. Interviews will be 45 minutes and conducted on an ongoing basis until we have reached saturation for identified themes. We anticipate requiring up to 10 interviews each at site and will divide them evenly among clinicians and patients. Participants will be compensated for the time they spend participating in qualitative interviews. [name] is an expert in qualitative research and will lead this effort following well-established methods.

**Quantitative** data will also be collected from stakeholders via written questionnaires. Among patients, at month 12 we will assess: general helpfulness of the program for improving their health (rated on a scale of 1 to 10), and trust in the ACC or CHW, measured with adapted items from the CAHPS. Among all clinicians in the participating sites, at study month 30 we will assess general helpfulness of the program for improving their patients' health, trust in the ACC or CHW, quality of the communication with the ACC/CHW, helpfulness of EMR-based support tool and barriers to using it. We will further assess clinicians' use of the decision support tool through electronic inquiries of the EMR. These will include the proportion of encounters in which the PCPs used the decision support tools, what elements they used or actively disregarded, and when they were used. Assessments of ACC activities will include reviews of their documentation on a random selection of 20 cases for each ACC and CHW beginning in study month 25. These will include the number and frequency of contacts per patient, the duration of visits and calls, the number of calls required to make contact with a patient for each planned encounter, the number of missed and kept scheduled in-person meetings, the number and subject of topics addressed during in-person encounters, and the frequency of documented exchanges between the ACC/CHW and PCP. The RAs will use a standardized chart abstraction form.

- **Retention Materials.** We will send winter holiday postcard to study participants. The card will thank them for their participation, letting each enrolled/consented person know that we appreciate their time and effort.

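### Assessor masking is not addressed, and the program-rating items scheduled at 3 and 12 months could reveal the arm to the interviewer before or during later outcome collection

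*Protocol*

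**What the plan says.** All of the following is in Protocol section 5f, Stage II.

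- **Allocation.** The RA does the baseline interview first. Then "the PM will access a dedicated website that implements the algorithm to obtain the assignment" and tells the ACCs or CHWs (the clinic-based and home-based workers) of new patients in their arm. The text neither tells RAs the arm nor says they are to be kept unaware of it.
- **Mode of contact.** "Baseline and 12-month interviews in person, 3-month and 6-month interviews by phone".
- **Patient Perspectives of Services row.** Modified CAHPS/HCAHPS subscales on trust and nursing care share a cell with "Overall rating of intervention (Scale 1-10) Baseline, 3M, 12M".
- **Program expectations row.** "Exit survey at 12M"; the questionnaire is an attachment that is not reproduced.
- **Outcomes at the same contacts.** ACT, Mini-AQLQ, MARS and self-reported utilization are collected at baseline, 3, 6 and 12 months. Trigger items and hand-held FEV1 are taken at baseline and 12 months, as is inhaler technique, by "RA observation on placebo device using validated checklist".
- **Quantitative assessment of acceptance.** This "data will also be collected from stakeholders via written questionnaires". For patients at month 12 it covers program helpfulness on a 1 to 10 scale and "trust in the ACC or CHW, measured with adapted items from the CAHPS". The same paragraph has RAs abstract ACC and CHW records for sampled cases from study month 25.

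Neither document mentions masking of RAs or outcome assessors, the order of items within an interview, who administers the rating items, or whether one RA follows a patient throughout.

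**The concern.** In an open trial of a behavioral intervention, patients cannot be masked, so the masking that remains available is that of the person who scores or elicits the outcomes. Here it seems within reach, because the assignment goes from the project manager to the interventionists and need not pass through the RA.

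Questions about the study program work against that. A usual-care patient has no coach or health worker to rate, so a score in one case and a not-applicable answer in another tends to separate usual care from the active arms, which is the SAP's superiority contrast. Skipping the items in usual care would disclose just as much. The month-12 trust items concern the ACC or CHW, so they could also separate the two active arms.

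At stake is drift in whatever depends on the RA: checklist scoring, encouragement during an effort-dependent breathing test, and probing of unclear answers. If RAs expect the supported patients to do better, the drift favors the active arms in both usual-care comparisons.

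**Working it through.** **1. Schedule check.** The plan states no figure on this point, so the first step is to set the passages side by side (Protocol 5f, Measures table).

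| Contact | Mode | Rating and trust items | Outcomes at the same contact |
|---|---|---|---|
| Baseline | In person | Listed | All; before randomization |
| 3 months | Phone | Listed | ACT, Mini-AQLQ, MARS, self-reported utilization, self-monitoring |
| 6 months | Phone | Not listed | ACT, Mini-AQLQ, MARS, self-reported utilization |
| 12 months | In person | Listed, plus exit survey | As at 3 months, plus FEV1, inhaler technique, trigger items |

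- The baseline entry cannot apply to a rating of the intervention, because allocation follows: "After the RA has completed the baseline research interview, the PM will access a dedicated website". The row's time points therefore need correcting, whichever items they were meant for.
- Read as written, the 3-month rating precedes the 6- and 12-month outcomes, and the 12-month rating falls at the same time point as the 12-month outcomes. Disclosure is possible; the text does not establish that it occurs.
- Carry-over from month 3 needs the same RA at a later contact, or answers shared between RAs. Section 5f speaks of four RAs and gives no rule on who follows whom. Section 5h gives RAs access to one tracking database but does not say that arm or answers are held there.
- Not exposed through the interview: ED visits and hospitalizations from the SPARCS registry, and appointment keeping, which comes from chart review.

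This table follows the protocol's schedule. The SAP's Aim 1 text uses 14 weeks and 9 months, a separate discrepancy on which this point does not depend.

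**2. Illustration of sensitivity.** The documents give no drift, so 0.1 and 0.2 SD are assumptions. Take no true effect, one comparison of an active arm with usual care, a simple two-sample test without clustering, and the SAP's 15% dropout.

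- *Patients per arm.* Protocol section 5c states a total of 405, but its site targets sum to 175 + 175 + 100 = 450. From 450: 150 × 0.85 = 127.5, taken as 127. From 405: 135 × 0.85 = 114.75, taken as 115.
- *Shift of the test statistic* = d / √(2/n). For n = 127: 0.1/0.1255 = 0.80 and 0.2/0.1255 = 1.59. For n = 115: 0.1/0.1319 = 0.76 and 0.2/0.1319 = 1.52.
- *Rejection probability* = P(Z > z − shift) + P(Z < −z − shift), with z = 1.960 at two-sided 5% and 2.241 at 2.5%. The SAP plans a Bonferroni correction without a divisor; 0.05/2 is assumed for the second case.

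| Patients per arm | Drift | At 5% | At 2.5% |
|---|---|---|---|
| 127 | 0.1 SD | 12.5% | 7.5% |
| 127 | 0.2 SD | 36% | 26% |
| 115 | 0.1 SD | 12% | 7% |
| 115 | 0.2 SD | 33% | 23% |

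On Table 5's FEV1 scale (SD 5, target difference 5), 0.2 SD is 0.2 × 5 = 1 point, or 1/5 = 20% of the target. FEV1 is a secondary outcome in the SAP.

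**The case against.** - **No masking was promised.** Correct. Having the project manager obtain the assignment after baseline is allocation concealment, and the trial describes itself as pragmatic. A reader might infer that the interview content breaches a safeguard the plan had set up. The documents do not support that: this is an omitted safeguard.
- **Disclosure is not shown.** A reader might also infer that interviewers will know every patient's arm from month 3. That goes too far. It needs the same RA or shared answers, and a 1 to 10 score alone does not tell ACC from CHW.
- **The 3-month entry is doubtful.** One schedule covers three items, and its baseline entry is impossible for a rating of the intervention. The schedule may have been meant for the general care subscales only, and the acceptance paragraph mentions month 12 alone. This stands as a reason to clarify the row; as written, it still lists 3 months.
- **The 12-month items are already written.** Largely so for program helpfulness and trust. But who hands out and collects the form, and when in the visit, is not stated, and the exit survey's mode cannot be seen.
- **Masking RAs would achieve little.** Patients know their arm, may mention a coach or a home visit, and answer ACT, Mini-AQLQ and MARS themselves. That bias would remain. RA abstraction of ACC and CHW records is a further route to the arm. This limits the gain without removing it for technique scoring, FEV1 coaching and probing.
- **The drift is assumed.** Agreed: the rejection rates show sensitivity and do not predict this trial's bias.

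**Conclusion.** The point holds as an omitted safeguard that is cheap to add. The plan does not say whether outcome collectors are masked, sets no item order, and schedules items that can reveal the arm at or before later outcome collection.

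The outcomes mainly exposed are RA-scored inhaler technique (not named in the SAP), hand-held FEV1, and interviewer-probed answers to the self-report scales. This assumes that RAs conduct the follow-up phone interviews and the 12-month spirometry, which the protocol implies but does not state. Registry utilization is outside the problem.

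The size cannot be derived from the documents. Across both totals and both alpha levels, an assumed drift of 0.1 SD gives 7% to 12.5% false rejection and 0.2 SD gives 23% to 36%. How much drift, if any, would come from these items alone is unknown.

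**What to change.** 1. **Correct the row.** Give each item in the Patient Perspectives row its own time points, and remove the rating of the intervention at baseline.
2. **3 months.** Ask the rating and trust items after all outcome items, or send them as a written form returned to the project manager. Asking them last protects that call only; the written form also protects the later contacts.
3. **12 months.** Give the written rating and trust items and the exit survey as a sealed form, only after ACT, Mini-AQLQ, MARS, utilization, trigger items, FEV1 and the inhaler checklist are recorded.
4. **State the rule.** Say that RAs who collect outcomes are kept unaware of arm where feasible, and name who administers the rating items.
5. **Record abstraction.** Do not have an RA abstract ACC or CHW records for patients whom that RA has still to assess.
6. **Check it.** Have the RA record a guess of the arm before the sealed form is given out, and report the guesses by arm.

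The cost is a change of order and mode, some care in assigning abstraction work, and one extra item for the RA, with no added visits. A mailed 3-month rating will probably get a somewhat lower response than a phone item. Patients' own reporting bias is not removed and should be acknowledged when results are reported.
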